#### **Investigational Agent(s)/How supplied:**

Drug name: Tranexamic Acid

Pharmaceutical company name: Apollo Pharmaceuticals USA Inc.

# **ABBREVIATIONS**

AE Adverse Event

CTSU Clinical Traisl Support Unit IRB Institutional Review Board

[figure not shown]
IV Intravenously

PI Pincipal Investigator
SAE Serious Adverse Event
TXA Tranexamic Acid
UaP Unanticipated Problem

	presented as frequency counts and percentages and analyzed using Fisher's exact test.				
	PISHEL S CARCILLEST.				

# STUDY SCHEMA

#### 1.0 BACKGROUND AND RATIONALE

Reduction mammoplasty and gender-affirming mastectomy are two common plastic surgery operations that are generally performed in relatively healthy patients in the outpatient setting. Although these procedures are relatively safe and have a low complication profile, reoperations can occur due to hematomas. The reported incidences of hematoma following reduction mammoplasty and gender-affirming mastectomy are around 3%-9% and 5%-10%, respectively. Most clinically significant hematoma will require operative washout or aspiration. If left untreated, hematomas can lead to nipple necrosis and skin flap compromise which can negatively impact patient satisfaction and aesthetic outcome.

Tranexamic acid (TXA) has emerged over the past decade as an adjunctive pharmacologic agent to reduce intraoperative blood loss and prevent post-operative bleeding. Its mechanism involves inhibition of the conversion of plasminogen to plasmin which then prevents the breakdown of fibrin clots. The efficacy of tranexamic acid has been demonstrated in cardiac surgery, orthopedic surgery, spine surgery. However, the use of tranexamic acid has not been routinely adapted into plastic surgery practice. There have been some studies assessing the use of tranexamic acid in plastic surgery procedures, including facial aesthetic surgery, craniofacial surgery, and breast reconstruction. In addition, the route of administration can include intravenous, oral, or topical. Some believe that the topical use of tranexamic acid provides a direct hemostatic benefit during surgery while decreasing systemic absorption. The concentration of topical tranexamic acid has been reported from 1.5% to 3% in orthopedic surgery and aesthetic surgery. Currently, the data suggests that tranexamic acid decreases intraoperative blood loss, postoperative bruising, and surgical drain output. However, there is a paucity of randomized prospective data on the efficacy of topical tranexamic acid in reducing clinically significant reoperative hematomas in breast surgeries.

This is a randomized control trial evaluating the efficacy of intraoperative topical tranexamic acid use in reduction mammoplasty and gender-affirming mastectomy. The primary outcome measure is the incidence of hematomas requiring operative intervention or aspiration. Secondarily, the occurrence of major thromboembolic events and other major complications will be assessed. This study hopes to further elucidate the safety and efficacy of topical tranexamic acid use in routine breast plastic surgery operations.

# 2.0 STUDY DESIGN, OBJECTIVES AND OUTCOME MEASURES

#### 2.1 Primary Objectives

To evaluate the safety and efficacy of topical tranexamic acid use in preventing hematomas in routine breast plastic surgery operations

Primary Outcome Measure:

1. Incidence of hematoma requiring operative intervention

#### 2.2 Secondary Objectives

To assess the safety profile of topical tranexamic acid when used as an intraoperative surgical irrigation

Seconary Outcome Measure:

- 1. Number of subjects experienging major thromboembolic events related to the study drug
- 2. Number of subjectrs experiencing major complicatios other than hematoma

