# 9.0 STATISTICAL CONSIDERATIONS

Sample size calculation was performed for a 50% reduction in hematoma requiring operative intervention or aspiration. The study would have 80 percent power to detect the expected 50 percent risk reduction (assuming  $\alpha = 0.05$ ,  $\beta = 0.20$ , n1:n2 of 1:1) if 250 patients are enrolled in each cohort.

Descriptive statistics of demographics and clinical characteristic of patients will be calculated. The descriptive statistics will be compared between the two treatment arms to assess any obvious imbalance in risk factors, despite the use of randomization.

A primary goal of the study is to evaluate the rate of hematoma requiring operation washout or aspiration in patients who receive topical TXA versus patients who do not receive topical TXA intraoperatively during breast reduction or gender-affirming mastectomy. This data will be presented as frequency counts and percentages and analyzed using Fisher's exact test. A value of p < 0.05 is considered statistically significant.

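### Safety is a stated objective, but Section 9.0 plans no analysis or confidence interval for it, and the synopsis's Fisher test is close to uninformative for thromboembolic events at 250 per arm

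*Combined protocol and SAP*

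**What the plan says.** **Objectives.** Section 2.1 gives the primary objective as "To evaluate the safety and efficacy of topical tranexamic acid use in preventing hematomas in routine breast plastic surgery operations", although its only outcome measure is hematoma. Section 2.2 is about safety alone: "To assess the safety profile of topical tranexamic acid when used as an intraoperative surgical irrigation". It has two measures: "Number of subjects experienging major thromboembolic events related to the study drug" and "Number of subjectrs experiencing major complicatios other than hematoma".

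**Analysis.** The Statistical Methodology row of the synopsis says that primary and secondary outcomes will be "presented as frequency counts and percentages and analyzed using Fisher's exact test". Section 9.0 covers baseline description, the sample size and the hematoma comparison. It does not mention the secondary outcomes. Its sentence "A value of p < 0.05 is considered statistically significant" closes the hematoma paragraph. The only power statement, "The study would have 80 percent power to detect the expected 50 percent risk reduction", also concerns hematoma and rests on 250 patients per arm.

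**Analysis set.** Section 6.2 limits the safety and tolerability analyses to subjects who received study drug. It refers the reader to Section 8.0, which is the drug information section.

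**Other safety provisions.** Adverse events are collected to 30 days (Sections 6.1 and 7.1), graded and attributed (7.3), and reviewed by the study team at least quarterly (10.0). The documents state no confidence interval, margin, acceptable event rate or numerical safety criterion.

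**The concern.** A significance test asks whether the data contradict equal rates. A safety objective asks how large an excess the data still allow. For a rare event and 250 patients per arm these questions come far apart: the test can hardly reject, so failure to reject says little. If only counts, percentages and a p-value are planned, the trial report need not say what size of harm has been excluded.

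Two features of the text make the between-arm test harder to interpret. The thromboembolic outcome counts only events attributed to study drug, which a patient in the non-TXA arm cannot have, so the control count is zero by definition. And Section 6.2, read literally, leaves the safety analysis without a comparator.

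**Working it through.** **Inputs.** From the documents: 250 per arm and 1:1 allocation (Sections 9.0 and 4.2), Fisher's exact test for the secondary outcomes (synopsis), and a level of 0.05 (Section 9.0). Assumed: a two-sided test, the same 0.05 level for the safety outcomes, no losses, and all safety event rates, because the documents give none.

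**The plan's own figure.** The one stated calculation is for hematoma and gives no control rate. The usual formula is n = [1.96·√(2p̄q̄) + 0.8416·√(p₁q₁ + p₂q₂)]² / (p₁ − p₂)². With 10% vs 5%, (0.7301 + 0.3121)² / 0.0025 gives 435 per arm; with 3% vs 1.5% it gives 1534. So 250 is not reproduced at the 3% to 10% range in Section 1.0. That is a separate matter. Only the 250 per arm is carried forward, and there is no safety figure to reproduce.

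**Step 1: what Fisher's test needs.** With c = 0 control events and t TXA events, the two-sided p-value is 2·C(250,t)/C(500,t).
- t = 5: 2 × (250·249·248·247·246)/(500·499·498·497·496) = 2 × 0.0306 = 0.061.
- t = 6: 2 × 0.0306 × 245/495 = 0.030.

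So 5 vs 0 (2.0% vs 0%) is not significant and 6 vs 0 is. With 1 control event the test needs 8 TXA events (p = 0.037); with 2 it needs 10 (p = 0.036). These thresholds require no assumed event rate.

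**Step 2: exact power.** Power = Σ Bin(t; 250, p_TXA)·Bin(c; 250, p_control), summed over all tables with Fisher p < 0.05.

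| Outcome | Assumed control vs TXA rate | Power |
|---|---|---|
| Thromboembolic | 0.2% vs 1% | 2.6% |
| Thromboembolic | 0.5% vs 1% | 1.3% |
| Thromboembolic | 0.5% vs 1.5% | 6.5% |
| Thromboembolic | 0.5% vs 2% | 16% |
| Thromboembolic | 1% vs 2% | 6.8% |
| Thromboembolic | 1% vs 3% | 24% |
| Other major complications | 2% vs 4% | 18% |
| Other major complications | 5% vs 10% | 51% |
| Other major complications | 10% vs 20% | 86% |

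If the control count is zero by definition, power is P(X ≥ 6) with X ~ Bin(250, p_TXA): 4.1% at 1%, 38% at 2% and 76% at 3%. That compares attributed events with a structural zero and is not a comparison of risks.

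**Step 3: what intervals would show.** For 0 of 250, the Clopper-Pearson two-sided 95% upper limit is 1 − 0.025^(1/250) = 1.46%. For 1 of 250 it is 2.21%, and for 2 of 250 it is 2.86%.

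The Newcombe interval combines the Wilson limits (l, u) of the two arms: lower = d − √[(p₁ − l₁)² + (u₂ − p₂)²], upper = d + √[(u₁ − p₁)² + (p₂ − l₂)²]. For 3 vs 1, the Wilson limits are 0.41% to 3.47% and 0.07% to 2.23%, and d = 0.8 points. The interval is −1.2 to +3.1 points.

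| TXA vs control events | Fisher p | 95% interval for the difference (points) |
|---|---|---|
| 0 vs 0 | 1.00 | −1.5 to +1.5 |
| 3 vs 1 | 0.62 | −1.2 to +3.1 |
| 5 vs 1 | 0.22 | −0.6 to +4.2 |
| 5 vs 0 | 0.061 | +0.1 to +4.6 |

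Every row is non-significant by Fisher's test, yet the rows differ widely in the excess they leave open.

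**The case against.** The other side has five fair points.

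- A reader might infer that the plan would declare TXA safe on a non-significant result. The documents do not say so. They contain no safety hypothesis, no non-inferiority claim and no rule linking a p-value to a safety conclusion, and the synopsis labels the trial a feasibility study.
- A reader might take p < 0.05 as a safety decision rule. That sentence belongs to the hematoma paragraph. Carrying it over to outcomes named only in the synopsis is plausible, but it is an inference.
- It would be wrong to say that safety rests on a p-value alone. Counts and percentages, adverse event grading and attribution, and quarterly review are also planned.
- Near-zero power cannot be claimed for both outcomes. Other major complications are undefined and may be common, in which case the test has moderate or good power for a doubling.
- Low power for rare harms is usual in trials sized for efficacy, and intervals can be computed later from published counts.

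All five stand as limits on the point. They do not remove it: none of the other provisions is a between-arm inferential criterion, and Fisher's test remains the only inferential method named for a stated objective. The last point holds only if events are counted in both arms on the same basis, which the attribution wording and Section 6.2 put in doubt. Those two passages also mean that adding intervals without changing the count would put precise-looking limits on an invalid contrast.

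**Conclusion.** The concern holds for thromboembolic events. At 250 per arm, Fisher's test needs at least 6 events against none, and has about 3% to 24% power for assumed rates from 0.2% vs 1% to 1% vs 3%; some smaller excesses give still less. A non-significant result would therefore not show what excess harm has been ruled out, and the plan specifies nothing else that would. The event thresholds and the 1.46% upper limit for 0 of 250 depend only on the sample size and the test; the power figures depend on the assumed rates.

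For other major complications, only the absence of an interval and of any analysis in Section 9.0 applies. This is an inexpensive improvement to the analysis plan. It does not show that the sponsor intends to misread the safety data, and it does not call for a larger trial.

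**What to change.** In Section 9.0, add an analysis of the secondary outcomes:

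1. Report each outcome by arm as count, percentage and exact (Clopper-Pearson) 95% confidence interval, and the between-arm risk difference with a 95% interval (for example Newcombe). Label any Fisher p-value as supplementary. State that the interval leads, since the two can disagree (5 vs 0 above).
2. Count major thromboembolic events in both arms regardless of attribution, with attribution reported separately. Section 6.1 already collects these events to 30 days after surgery, so no new data should be needed.
3. Reconcile Section 6.2 with this comparison so that the safety analyses include the non-TXA arm, and correct its cross-reference to Section 8.0.
4. State that non-significance is not evidence of safety, and that 0 of 250 excludes only event rates above about 1.5%.

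The cost is a few lines of SAP text and code, and a more modest safety conclusion. The sample size does not change.

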#### 3.0 SUBJECT ELIGIBILITY

Subjects must meet all of the selection criteria to be enrolled to the study. Study treatment may not begin until a subject has been consented and meets the eligibility criteria.

#### 3.1 Inclusion Criteria

- Patients aged 18 or over who are undergoing bilateral breast reduction or bilateral gender-affirming mastectomy
- o For patients undergoing bilateral breast reduction, any skin incision pattern or pedicle is acceptable
- o For patients undergoing bilateral gender-affirming mastectomy, any skin incision and mastectomy type is acceptable
- o Subjects must be able to understand/read/speak English

#### 3.2 Exclusion Criteria

- Active thromboembolic disease or history of intrinsic risk of thrombosis or thromboembolism, including retinal vein or artery occlusion
- Current use of systemic anticoagulation
- Hypersensitivity to tranexamic acid
- Concomitant use of combined hormonal contraceptives
- Use of factor IX complex concentrates, anti-inhibitor coagulant concentrates or all-trans retinoic acid
- History of acquired defective color vision
- History of subarachnoid hemorrhage
- Pregnancy
- History of renal impairment or serum Cr>1.5mg/dL

# 4.0 SUBJECT SCREENING, ENROLMENT, AND RECRUITMENT

#### 4.1 Patient Screening and Recruitment

Once a patient has been scheduled for either breast reduction or gender-affirming mastectomy, a member of the study team will conduct screening based on eligibility criteria and contact the patient using an IRB approved recruitment script to discuss the study and participation. Initial contact will either be made remotely, using the phone

number or email address listed in MiChart or a message via the patient portal, or if time allows, in-person following the consultation in a private area. If they agree to participate, they will be asked to sign an electronic consent form. Hard copies of the consent document will be available also.

#### 4.2 Randomization

Patients will be randomized in a 1:1 ratio to either the TXA arm or the non-TXA arm. Randomization will occur pre-operatively in REDCap, the study's data management system.

# 4.3 Blinding

This study will be single-blinded. Patients will be blinded to the treatment. The surgical team will not be blinded.

#### 5.0 TREATMENT PLAN

# 5.1 Drug dministration plan

The surgical procedure will be performed according to standard practice determined by each individual surgeon. Topical TXA will be administered intraoperatively as a surgical irrigation. For patients randomized to the TXA arm, the breast pockets will additionally be irrigated with 150 cc of 2.67% TXA (75 cc in each breast). The TXA solution will be allowed to be sit in the breast pocket for 15 minutes and then removed after 15 minutes. In the non-TXA arm, breast pockets will not receive additional irrigation.

Table 1. Drug Administration Plan

Agent	Dose	Route	Schedule
Tranexamic	Total dose: 150 cc of 2.67% TXA	Topical	Administer once intraoperative
Acid	Dose per breast: 75 cc of 2.67% TXA		as a surgical irrigation

# 5.2 Toxicities and Dosing Delays/Dose Modifications

Each subject will be assessed for the development of toxicity according to the Time and Events Table (Section 6.3).

#### **5.3** Concomitant Medications/Treatments

Concomitant drugs and/or treatments that are prohibited including the following:

- Concomitant use of systemic anticoagulation
- Concomitant use of combined hormonal contraceptives
- Concomitant use of factor IX complex concentrates, anti-inhibitor coagulant concentrates or all-trans retinoic acid

#### 5.4 **Duration of Therapy**

The study drug will be administered once intraoperatively with a total duration of 15 minutes.

Administration of treatment may continue unless one of the following criteria apply:

- Inter-current illness that prevents further administration of treatment
- Unacceptable adverse event(s)
- Subject voluntarily withdraws from treatment OR
- General or specific changes in the subject's condition render the subject unacceptable for further treatment in the judgment of the investigator

#### 5.5 Off Treatment Criteria

Subjects will be removed from protocol therapy when any of the criteria listed in Section 5.4 apply. Subjects who discontinue treatment will continue protocol specific follow-up procedures as outlined in Section 5.6. The only exception to this requirement is when a subject withdraws consent for all study procedures or loses the ability to consent freely.

# 5.6 Duration of Follow-Up

Patients will be followed for 4 weeks postoperatively. The follow-up timeline will be dictated by each surgeon's standard practice, but will generally consist of 2 visits, one approximately 1 week after surgery and a second approximately 4 weeks after surgery.

#### 5.7 Off Study Criteria

Subjects can be taken off study at any time at their own request, or they may be withdrawn at the discretion of the investigator for safety, behavioral, or administrative reasons. The reason(s) for discontinuation from study will be documented and may include:

- 1. Subject withdraws consent (termination of treatment and follow-up);
- 2. Loss of ability to freely provide consent through imprisonment;
- 3. Subject is unable to comply with protocol requirements;
- 4. Treating physician judges that continuation on the study would not be in the subject's best interest;
- 5. Subject becomes pregnant;
- 6. Lost to Follow-up. If a research subject cannot be located for 1 year, the subject may be considered "lost to follow-up." All attempts to contact the subject during the one year must be documented;
- 7. Termination of the study by the investigators or the University of Michigan
- 8. Subject completes protocol treatment and follow-up criteria.

# 5.8 Subject Replacement

The subjects will not be replaced.

#### 6.0 STUDY PROCEDURES AND EFFICACY ASSESSMENT

#### 6.1 Study Procedures and Efficacy Assessments

Surgical technique

Patients will undergo their breast reduction surgery or gender-affirming mastectomy based on standard surgical technique by each surgeon. For patients undergoing breast reduction, there are no requirements on the method of skin incisions or type of pedicle used. This decision will be per individual surgeon judgement. For patients undergoing gender-affirming mastectomy, there are also no requirements on the method of skin incision and type of mastectomy. This will be per individual surgeon judgement. Once the surgeon has completed resecting the breast tissue, the weight of the resected tissue will be recorded. Hemostasis will be achieved in the standard fashion using electrocautery and the surgical sites may be irrigated according to each surgeon's preference. Next, for patient randomized to the TXA arms, the breast pockets will additionally be irrigated with 150 cc of 2.67% TXA (75 cc in each breast). The TXA solution will be allowed to be sit in the breast pocket for 15 minutes and then removed after 15 minutes. In the non-TXA arm, each breast pocket will not receive additional irrigation. The surgical sites will then be closed in a fashion that is determined by the individual surgeon. The use of postoperative drains and surgical compression garment will also be per the individual surgeon.

#### Follow-up

Patients will be followed for 4 weeks postoperatively. The follow-up timeline will be dictated by each surgeon's standard practice, but will generally consist of 2 visits, one approximately 1 week after surgery and a second approximately 4 weeks after surgery. The primary and secondary outcomes of the study will be collected by a study team member via chart review.

Any adverse events will also be collected up to 30 days after surgery. Adverse events include the following:

- Hematoma
- Seroma
- Re-operation
- Infection
- Wound dehiscence
- Skin necrosis
- Rash
- Thromboembolic events (DVT, PE)
- Hypersensitivity reaction
- Seizures
- Vision change

#### 6.2 Safety/Tolerability

Analyses will be performed for all subjects having received the study drug (See Section 8.0).

#### 6.3 Time and Events Table

Study Element	Pre-Op	Day of Surgery	Post-op (until 4 weeks after surgery)
Informed Consent	X		
Demographics	X		
Eligibility	X		
BMI	X		
Comorbidities	X		
Smoking status	X		
Study intervention		X	
Resection weight(s)		X	
Surgical technique (including		X	
incision type and pedicle type)			
Use of surgical drains		X	
Estimated blood loss		X	
Need for transfusion		X	
Use of postoperative		X	X
compression wrap or garments			
Surgical complications		X	X
Adverse events		X	X

#### 7.0 ADVERSE EVENTS

#### 7.1 Adverse Event Reporting Requirements

Adverse event (AE) monitoring and reporting is a routine part of every clinical trial and is done to ensure the safety of subjects enrolled in the studies as well as those who will enroll in future studies using similar agents. Data on adverse events will be collected from the time of the initial study treatment or intervention through 30 days after the last dose of study treatment or intervention. Any serious adverse event that occurs more than 30 days after the last study treatment or intervention and is considered related to the study treatment or intervention must also be reported. Serious Adverse Events (SAEs) will continue to be followed until:

- Resolution or the symptoms or signs that constitute the serious adverse event return to baseline;
- There is satisfactory explanation other than the study treatment or intervention for the changes observed; or
- Death.

The investigator is responsible for the detection, documentation, grading and assignment of attribution of events meeting the criteria and definition of an AE or SAE. The definitions of AEs and SAEs are given below. It is the responsibility of the principal

investigator to ensure that all staff involved in the trial is familiar with the content of this section.

Any medical condition or laboratory abnormality with an onset date before initial study treatment administration or intervention is considered to be pre-existing in nature. Any known pre-existing conditions that are ongoing at time of study entry should be considered medical history.

All events meeting the criteria and definition of an AE or SAE, as defined in Section 8.3, occurring from the initial study treatment administration or intervention through 30 days following the last dose of the study treatment or study intervention must be recorded as an adverse event in the subject's source documents and on the CRF regardless of frequency, severity (grade) or assessed relationship to the study treatment or intervention.

In addition to new events, any increase in the frequency or severity (i.e., toxicity grade) of a pre-existing condition that occurs after the subject begins study treatment or intervention is also considered an adverse event.

Review of AE and SAE data will be performed on a routine basis by the study team.

